APPENDIX 2. SAMPLE SAS PROGRAM FOR THE PRIMARY ANALYSIS FOR PRIMARY ENDPOINT USING ANCOVA MODEL

The analysis will employ of the following SAS procedures:

- For each analysis population or identified population for analysis, perform the MI for the population once. The MI results will be used for all analyses planned for the population.
- 100 datasets will be generated where missing data at intermediate visits will be imputed for each treatment group using non-missing data from all subjects within the treatment group by a Monte Carlo Markov Chain (MCMC) imputation model using the MCMC statement in the SAS PROC MI procedure. As a result, each dataset will only have missing ending data, or a monotone missing data pattern.
- For each dataset from the prior step, missing ending data will be imputed by a regression imputation model using the SAS PROC MI procedure with the REGRESSION option in the MONOTONE statement using the CCMV assuming that the missing values are MNAR. The regression imputation model includes an intercept and the slopes of the measurements from all previous visits for the imputation of subsequent visits.
- The resulting complete datasets from the prior step will be processed via a SAS DATA step to create change from baseline values for each treatment group at each visit.
- The resulting datasets will be analyzed using SAS PROC MIXED to perform the analysis of covariance for the primary efficacy endpoint by study visit.
- The SAS PROC MIANALYZE procedure will be used to combine the LS mean and treatment versus placebo difference estimates to produce the final analysis results.

Sample SAS code corresponding to the above steps appears below:

```
/******  
Multiple imputation assuming MNAR using complete case missing value pattern  
  
TRTn: Treatment (0=Placebo, 1=Ataluren)  
Cortico: Steriod use at randomization  
C6mwd: Baseline 6MWD categories  
Stand: Baseline stand from supine categories  
ITTfl: Identifier for ITT population  
*****/  
  
* 1st: Generate 100 datasets to impute missing interim data by treatment  
group using MCMC option;  
proc sort data=smwt; by trtn usubjid; run;  
proc MI data=smwt out=smwt_mono minimum=0 nimpute=100 minmaxiter=5000  
seed=93182;  
  WHERE ITTfl="Y";  
  BY trtn;  
  VAR SmwdWKBL SmwdWK12 SmwdWK24 SmwdWK36 SmwdWK48 SmwdWK60 SmwdWK72  
  SmwdWK96 SmwdWK120 SmwdWK144;  
  MCMC chain=multiple impute=monotone;
```

run;

* 2nd: Impute missing ending data using monotone statement with regression option and assuming MNAR using CCMV;

```
proc sort data=smwt_mono out=smwt_mono; by _imputation_ trtn usubjid; run;
proc MI data=smwt_mono out=smwt_ccmv minimum=0 nimpute=1 minmaxiter=5000
seed=93035;
  WHERE ITTfl="Y";
  BY _imputation_ trtn;
  VAR SmwdWKBL SmwdWK12 SmwdWK24 SmwdWK36 SmwdWK48 SmwdWK60 SmwdWK72 SmwdWK96
SmwdWK120 SmwdWK144;
  MONOTONE reg(/details);
  MNAR Model (SmwdWK12 SmwdWK24 SmwdWK36 SmwdWK48 SmwdWK60 SmwdWK72 SmwdWK96
SmwdWK120 SmwdWK144/Modelobs=CCMV);
run;
```

* 3rd: Create datasets for ANCOVA;

```
data smwt_reg;
  set smwt_ccmv;
  AWeek= 0; Avalimp=SmwdWK0; CFBimp=SmwdWK0-BL6mwd; output;
  AWeek=12; Avalimp=SmwdWK12; CFBimp=SmwdWK12-BL6mwd; output;
  AWeek=24; Avalimp=SmwdWK24; CFBimp=SmwdWK24-BL6mwd; output;
  AWeek=36; Avalimp=SmwdWK36; CFBimp=SmwdWK36-BL6mwd; output;
  AWeek=48; Avalimp=SmwdWK48; CFBimp=SmwdWK48-BL6mwd; output;
  AWeek=60; Avalimp=SmwdWK60; CFBimp=SmwdWK60-BL6mwd; output;
  AWeek=72; Avalimp=SmwdWK72; CFBimp=SmwdWK72-BL6mwd; output;
  AWeek=96; Avalimp=SmwdWK96; CFBimp=SmwdWK96-BL6mwd; output;
  AWeek=120; Avalimp=SmwdWK120; CFBimp=SmwdWK120-BL6mwd; output;
  AWeek=144; Avalimp=SmwdWK144; CFBimp=SmwdWK144-BL6mwd; output;
```

run;

...

* 4th: Conduct ANCOVA analysis on imputed datasets;

```
proc sort data=adsmwdimp out=adsmwdimp; by _imputation_; run;
ods exclude all;
proc mixed data=adsmwdimp method=REML;
  WHERE ITTfl="Y" and Aweek=144;
  BY _imputation_;
  CLASS Cortico Trtn C6mwd Stand;
  MODEL CFBimp=BL6MWD Trtn Cortico Stand C6MWD / CL;
  LSMEANS Trtn/ diff=control('0') cl alpha=0.05;
  ods output diffs=diff_mi lsmeans=lsm_mi;
run;
ods exclude none;
```

* 5th: Use Proc MIAnalyze to obtain final analyiss results;

* LS Means;

```
proc mianalyze parms(classvar=full)=lsm_mi;
  CLASS Trtn;
  MODELEFFECTS Trtn;
  ods output parameterestimates=lsm_out;
run;
```

* Treatment differences;

```
proc mianalyze parms(classvar=full)=diff_mi;
  CLASS Trtn;
  MODELEFFECTS Trtn;
  ods output parameterestimates=diff_out;
run;
```

The table below lists the random seeds to be used for the primary and secondary analyses and some additional seeds should they be required. The random seeds were created using SAS uniform generator RAND(“Uniform”) with a seed of 20220316.

| Endpoint/Analysis | Seed for Step 1 (impute missing interim data) | seed for Step 2 (impute missing ending data) |
|--|---|--|
| 6MWD (mITT, Section 6.2.1) | 91137 | 7262 |
| 6MWD (ITT, Section 6.2.1) | 1457 | 59445 |
| 10 Meter Run/Walk (mITT, Section 6.2.2) | 77829 | 5735 |
| 10 Meter Run/Walk (ITT, Section 6.2.2) | 47225 | 22804 |
| 4-stair climb (mITT, Section 6.2.2) | 89124 | 91655 |
| 4-stair climb (ITT, Section 6.2.2) | 65399 | 28168 |
| 4-stair descend (mITT, Section 6.2.2) | 10797 | 25074 |
| 4-stair descend (ITT, Section 6.2.2) | 65528 | 98908 |
| NSAA (mITT, Section 6.2.3) | 49813 | 69116 |
| NSAA (ITT, Section 6.2.3) | 70669 | 12277 |
| PUL (mITT, Section 6.3.1) | 88445 | 32933 |
| PUL (ITT, Section 6.3.1) | 44851 | 95936 |
| DMD Upper Limb PROM (mITT, Section 6.3.1) | 66837 | 18935 |
| DMD Upper Limb PROM (ITT, Section 6.3.1) | 66322 | 26365 |
| Myometry (ITT, Section 6.3.2) | 35523 | 63532 |
| If additional analyses need to be performed, seeds below will be used | | |
| Additional Analysis #1 | 1371 | 4851 |
| Additional Analysis #2 | 10065 | 77968 |
| Additional Analysis #3 | 51500 | 83604 |

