Baseline time to stand from supine also significantly predicts for change in 6MWD, independently of baseline 6MWD [Goemans 2016, Mazzone 2016], with poor performance on the time to stand from supine assessment increasing the risk of markedly negative changes in 6MWD and loss of ambulation. These results have identified time to stand from supine as an important additional prognostic factor of changes in 6MWD and more generally of disease progression [Mazzone 2016]. A threshold value of approximately 5 seconds appears to differentiate between patients who are likely to show stability or improvement versus those who are likely to decline [Goemans 2016]. These observations from natural history studies have been corroborated by analyses of data from our own previous placebo-controlled trials of ataluren.

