An ANCOVA model will also be used to evaluate the difference in change in 6MWD from baseline to Week 144 after missing data have been imputed via a pattern mixture model utilizing MI based on ITT population. The estimated treatment difference in change from baseline of 6MWD at Week 144 and the corresponding 95% CI will be provided. The ANCOVA model will include baseline concomitant corticosteroid type (deflazacort, prednisone/prednisolone), baseline 6MWD category (<300 meters, 300 to <350 meters, 350 to <400 meters, ≥400 meters), treatment, as well as baseline 6MWD as a covariate. The baseline time to stand from supine (<5 seconds, ≥5 seconds) will be included in the testing model in the ITT analysis. For this analysis, all 6MWD will be assigned to an analysis visit according to the analysis visit window described in Section 4.9. Any subjects who lose ambulation during the study will be assigned a 6MWT result of 0 meters for the visit in which the subjects lose ambulation and for all remaining visits while they participate in the study. For subjects with missing 6MWD due to other reasons, the missing assessments at post-baseline visits will be imputed using the pattern-mixture model MI assuming the missing values are missing not at random (MNAR) utilizing the complete case missing value pattern (CCMV - subjects who completed primary efficacy assessments without missing values). Detailed imputation method is described in [Appendix 2](#).

The example SAS code is listed below:

```
PROC MIXED data=<dataset> method=reml;  
  CLASS Cortico TTSTBLC Trt C6MWD;  
  MODEL CHG6MWD = Cortico TTSTBLC C6MWD Trt B6MWD /CL;  
  LSMEANS TRT / pdiff CL;  
RUN;
```

where

CHG6MWD = change from baseline in 6MWD at Week 144
B6MWD = Baseline 6MWD
C6MWD = Baseline 6MWD category
Cortico = Baseline concomitant corticosteroid type
TTSTBLC = Time to stand from supine category
Trt = Treatment group

The 6MWD values and the corresponding changes from study baseline values will be summarized by visit during overall treatment period based on ITT population. For these summaries, any subjects who lose ambulation during the study will be assigned a 6MWT result of 0 meters for the visit in which the subjects lose ambulation and for all remaining visits while they participate in the study.

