6.2.1.2. North Star Ambulatory Assessment - Total Scores

The NSAA consists of 17 activities, each scored as 0, 1, or 2. The sum of 16 scores (except for lifts head) will be used to form a total score [Mayhew 2013a]. Hereafter, this NSAA total score will be referred to as revised NSAA (rNSAA) total score. If an activity cannot be performed due to disease progression/LoA, a score of 0 will be assigned, and will not be considered as missing. If fewer than 13 of the 16 activities are performed, the total score will be considered missing. If from 13 to 16 activities are performed, the total score will be standardized by multiplying the sum of the scores in the x activities by 16/x.

The change from baseline in rNSAA total score at Week 72 based on the mITT population will be the second key secondary endpoint. An ANCOVA model will be used to evaluate the difference in change in rNSAA from baseline to Week 72 after missing data have been imputed via a pattern mixture model utilizing MI. The ANCOVA model will include factors of baseline

concomitant corticosteroid type (deflazacort, prednisone/prednisolone), baseline 6WMD category (<300 meters, 300 to <350 meters, 350 to <400 meters, \geq 400 meters), and treatment, and covariate of baseline rNSAA total score. The estimated difference in the change at Week 72 will be provided.

If both primary efficacy endpoint and the first key secondary endpoint are statistically significant at the 0.05 significance level, the rNSAA will be tested at the 0.05 (two-sided) significance level.

The same ANCOVA model will also be performed on linear transformation of the total score [Mayhew 2013a].

As a sensitivity analysis, rNSAA total score and linear score will be analyzed using a MMRM model with a random intercept. The MMRM model will include baseline concomitant corticosteroid type (deflazacort, prednisone/prednisolone), baseline 6WMD category (<300 meters, 300 to <350 meters, 350 to <400 meters, \geq 400 meters), treatment, visit (analysis visit as a categorical variable), the baseline rNSAA score as the covariate, as well as interaction of visit and treatment, and the interaction of visit and baseline rNSAA total score. The unstructured covariance matrix (UN) will be used in the MMRM model. Other types of covariance matrix (heterogenous Toeplitz, Toeplitz, and compound symmetric) will be explored in the case of non-convergence of UN.

A sample code is listed as below:

```
PROC MIXED data=<dataset> method=reml;  

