APPENDIX 2. SAMPLE SAS PROGRAM FOR THE PRIMARY ANALYSIS FOR PRIMARY ENDPOINT USING ANCOVA MODEL

The analysis will employ of the following SAS procedures:

- For each analysis population or identified population for analysis, perform the MI for the population once. The MI results will be used for all analyses planned for the population.
- 100 datasets will be generated where missing data at intermediate visits will be imputed for each treatment group using non-missing data from all subjects within the treatment group by a Monte Carlo Markov Chain (MCMC) imputation model using the MCMC statement in the SAS PROC MI procedure. As a result, each dataset will only have missing ending data, or a monotone missing data pattern.
- For each dataset from the prior step, missing ending data will be imputed by a regression imputation model using the SAS PROC MI procedure with the REGRESSION option in the MONOTONE statement using the CCMV assuming that the missing values are MNAR. The regression imputation model includes an intercept and the slopes of the measurements from all previous visits for the imputation of subsequent visits.
- The resulting complete datasets from the prior step will be processed via a SAS DATA step to create change from baseline values for each treatment group at each visit.
- The resulting datasets will be analyzed using SAS PROC MIXED to perform the analysis of covariance for the primary efficacy endpoint by study visit.
- The SAS PROC MIANALYZE procedure will be used to combine the LS mean and treatment versus placebo difference estimates to produce the final analysis results.

Sample SAS code corresponding to the above steps appears below:

```
/******  
Multiple imputation assuming MNAR using complete case missing value pattern  
  
TRTn: Treatment (0=Placebo, 1=Ataluren)  
Cortico: Steriod use at randomization  
C6mwd: Baseline 6MWD categories  
mITTfl: Identifier for mITT population  
*****/  
  
* 1st: Generate 100 datasets to impute missing interim data by treatment  
group using MCMC option;  
proc sort data=smwt; by trtn usubjid; run;  
proc MI data=smwt out=smwt_mono minimum=0 nimpute=100 minmaxiter=5000  
seed=93182;  
  WHERE mITTfl="Y";  
  BY trtn;  
  VAR SmwdWKBL SmwdWK12 SmwdWK24 SmwdWK36 SmwdWK48 SmwdWK60 SmwdWK72;  
  MCMC chain=multiple impute=monotone;  
run;
```

* 2nd: Impute missing ending data using monotone statement with regression option and assuming MNAR using CCMV;

```

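### Multiple imputation in Appendix 2 omits baseline covariates that the ANCOVA on the imputed data adjusts for; the effect is small and the remedy nearly free, and it matters most for the Week 144 ITT analyses

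*SAP*

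**What the plan says.** Appendix 2 of the open-label SAP describes two imputation steps. Gaps between observed visits are filled first by MCMC within treatment group. Missing values at the end of follow-up are then filled by regression: "The regression imputation model includes an intercept and the slopes of the measurements from all previous visits for the imputation of subsequent visits". That regression is fitted "utilizing the complete case missing value pattern", that is, on boys with no missing values.

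The sample code agrees with the text. Both PROC MI calls run within arm ("by _imputation_ trtn" in the second), and the variable list holds 6MWD values only: "VAR SmwdWKBL SmwdWK12 SmwdWK24 SmwdWK36 SmwdWK48 SmwdWK60 SmwdWK72 SmwdWK96" and then Weeks 120 and 144. The ANCOVA on the completed data has a longer list: "MODEL CFBimp=BL6MWD Trtn Cortico Stand C6MWD / CL".

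Appendix 2 of the double-blind SAP has the same design up to Week 72 ("The regression imputation model includes an intercept and the slopes of the measurements from all previous visits"). Its mITT ANCOVA adjusts for corticosteroid type, 6MWD category and baseline 6MWD. Section 6.1.3.2 adds time to stand in ITT.

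Protocol 11.3.2 explains why time to stand is a stratification factor: "Baseline time to stand from supine also significantly predicts for change in 6MWD, independently of baseline 6MWD".

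**The concern.** The imputation model is poorer than the analysis model it feeds. Among boys in the same arm with the same walking history, one who stands in under 5 seconds and one who takes 5 seconds or more receive draws from the same distribution, although the protocol expects the slower riser to decline faster. The slower riser is then imputed too high and the faster riser too low.

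Imputing within arm protects the treatment contrast only when dropout by stratum is alike in both arms, and nothing in the documents assures that. If the mixes differ, part of the difference passes into the estimated treatment effect, in favour of the arm that loses more slow-to-stand boys.

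The most exposed analyses are those at Week 144 for rNSAA, PUL, PROM and myometry (open-label SAP 6.2.3, 6.3.1, 6.3.2). ANCOVA after imputation is the only inferential model named there for the total score or parameter. Follow-up is twice as long as in the double-blind period, and no dropout rate is given for the open-label period.

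**Working it through.** **1. The plan's own figure.** The documents give no figure for the effect of the imputation model. The nearest scale is the ANCOVA-after-MI row of Table 1 in the Changes from Planned Analysis document (mITT, Week 72): 9.10 m, SE 13.1 m. Dividing by 72 weeks gives 9.10/72 = 0.126 and 13.1/72 = 0.182 m/week, which match the stated 0.13 and 0.182.

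**2. The two models side by side (6MWD, ITT).**

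| Predictor | Both imputation steps | ANCOVA |
|---|---|---|
| Baseline 6MWD | yes, linear | yes |
| 6MWD category | not as such; largely carried by baseline 6MWD | yes |
| Corticosteroid type | no | yes |
| Time to stand | no | yes |
| Other 6MWD visits | yes | no |

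So for 6MWD two of the three strata are in effect absent. If the other endpoints follow the same pattern (the sample code shows 6MWD only), 6MWD category has no representative there either.

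**3. Mechanism.** With stratum share π, dropout proportion d and mean imputation error e, the shift in one arm's mean is about Σ π·d·e over strata. The shift in the arm difference is that sum in one arm minus the sum in the other. It is zero when d by stratum is the same in both arms.

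**4. Simulation at Week 144** (400,000 boys per scenario; within-arm regression imputation from completers, then the SAP's ANCOVA). None of the inputs comes from the documents:
- 60% stand in 5 s or more.
- Baseline SD is 60 m, random-slope SD 0.7 m/week and test noise SD 25 m.
- Decline is 0.3 to 1.0 m/week faster in the 5 s or more stratum, and the corticosteroid gap is 30% of that.

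Shift in the arm difference, in metres:

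| Dropout, <5 s / ≥5 s, one arm v the other | Last visit Weeks 12–120 | Weeks 12–36 | Weeks 72–96 |
|---|---|---|---|
| Same mix in both | about 0 (within 0.2) | about 0 | about 0 |
| 10%/15% v 15%/10% | 0.2–0.9 | 1.3–1.8* | 0.1–0.2 |
| 5%/20% v 20%/5% | 0.6–2.9 | 1.6–5.7 | 0.1–0.7 |
| 5%/40% v 40%/5% | 1.6–7.0 | up to 14.7 | 0.1–1.8 |

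*At stratum gaps of 0.7 and 1.0 m/week.

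With the strata in the imputation model, every shift is within 0.3 m of zero, which is simulation noise.

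For a single dropout, with last visits spread over Weeks 12–120, the error is about 5 to 22 m too low (under 5 s) or 3 to 15 m too high (5 s or more). If the last visit was at Weeks 72–96, it is at most about 5 m.

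**5. Hand check of one cell.** Take the 0.7 m/week gap, early dropout, 5%/20% v 20%/5%, with simulated errors of −31.2 m and +19.3 m:
- First arm: 0.4×0.05×(−31.2) + 0.6×0.20×19.3 = −0.62 + 2.32 = +1.69 m.
- Second arm: 0.4×0.20×(−31.2) + 0.6×0.05×19.3 = −2.50 + 0.58 = −1.92 m.
- Difference: about 3.6 m, against 3.92 m simulated. The formula uses errors averaged over the arms, so exact agreement is not expected.

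**6. Second simulation** (N = 359; 65% at 5 s or more; 1.1 m/week gap; slow-to-stand boys twice as likely to drop out on ataluren and half as likely on placebo). At 5%, 10% and 20% dropout, the shift without and with the strata was:
- Week 72: 0.36/0.03, 0.74/0.06 and 1.56/0.03 m.
- Week 144: 0.55/0.12, 1.13/0.15 and 2.53/0.25 m.
- Same mix in both arms, 20% dropout, Week 144: −0.15/−0.17 m.

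For rNSAA without the strata, the shift was 0.02 to 0.07 points, and about zero with them.

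**7. Scale.** The strong-imbalance range of 0.6 to 2.9 m is 5% to 22% of 13.1 m (0.6/13.1 and 2.9/13.1). This is a yardstick only: the SE is for mITT at Week 72 and the shift is for ITT at Week 144.

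**The case against.** The case for leaving the plan alone has several sound parts.

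- *Role.* For 6MWD, ANCOVA after imputation is a sensitivity or second model. The main ITT model is the categorical MMRM, which contains all three strata. This stands.
- *The gated rNSAA test.* The double-blind SAP (6.2.1.2) assesses the "difference in change in rNSAA from baseline to Week 72 after missing data have been imputed" in mITT. A reader might infer that ignoring time to stand undermines that test. It does not: every mITT boy stands in 5 s or more, so the factor is constant. Only corticosteroid type, on which Protocol 11.3.2 calls the comparative evidence mixed, and three 6MWD bands remain.
- *Own history.* Interim gaps borrow from all visits, and a boy's own visits reveal most of his course. Boys who lose ambulation are assigned 0 m while they participate, and neither simulation is recorded as modelling that rule. This stands, and supports a small effect.
- *Inputs.* The stratum gaps are assumed, and 1.1 m/week exceeds the 1.0 m/week drug effect in the sample-size section. The only documented discontinuation rate is about 5%, where the second simulation gives 0.36 m at Week 72, or 3% of 13.1 m. This stands for Week 72. No rate is given for Week 144.
- *Imbalance.* Nothing documents opposite dropout patterns. True, but they need only differ: 5%/20% against 15%/15%, all early, gave 2.0 to 2.8 m at gaps of 0.7 and 1.0 m/week.
- *Timing.* Week 72 results are already reported, so changing that imputation now would be another change made after unblinding. This stands, and shapes the remedy.

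**Conclusion.** The mismatch between imputation and analysis models is plain in text and code, and worth correcting as a minor improvement. Under assumed moderate to strong imbalance in who drops out, with dropout spread over the visits, the arm difference in 6MWD moves by about 0 to 3 m. It moves by several metres or more only if dropout is early or extreme, and by about zero if both arms lose the same mix. These sizes rest on assumed stratum effects and dropout patterns.

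Three stronger inferences are not supported. The main 6MWD result is not affected, because the MMRM carries the strata. The 6MWD imputation does not lose all three strata, because baseline 6MWD is in it. Not every dropout is badly imputed, because the error shrinks as more visits are observed. That the other endpoints also lack baseline 6MWD is an inference from sample code for one endpoint, and the SAP should settle it.

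**What to change.** In Appendix 2 of the open-label SAP, for the ITT Week 144 analyses:

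1. Put the ANCOVA baseline covariates first in the variable list of both PROC MI steps, coded as numeric indicators in the MCMC step: corticosteroid type, time-to-stand category and 6MWD category.
2. For rNSAA, the timed tests, PUL, PROM and myometry, also add baseline 6MWD, and state that the imputation follows this pattern.
3. Omit any indicator that is constant in the population analysed.
4. State a rule for collapsing sparse cells. Section 4.10 merges a stratum only when it holds a single arm, so it does not cover this.
5. Tabulate dropout by arm and stratum, so that readers can see whether the issue arises.

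The by-arm imputation, the complete-case pattern, the 100 imputations and the seeds can stay. For Week 72, run the corrected imputation only as a labelled supplementary analysis.

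The cost is a few lines of SAP text and 1 + 1 + 3 = 5 indicator columns, plus baseline 6MWD for the other endpoints. All derive from data given to the IRT before randomisation (Protocol 4.3). The open-label SAP still places the final lock in the future, so on its text the change can be made beforehand.

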APPENDIX 3. LABORATORY RELATED CTCAE SEVERITY GRADE

| AE Term | Grade 1 | Grade 2 | Grade 3 | Grade 4 | Grade 5 |
|---|--|---|---|---|---------|
| White blood cell decreased | <LLN - 3000/mm ³ ; <LLN - 3.0 x 10 ⁹ /L | <3000 - 2000/mm ³ ; <3.0 - 2.0 x 10 ⁹ /L | <2000 - 1000/mm ³ ; <2.0 - 1.0 x 10 ⁹ /L | <1000/mm ³ ; <1.0 x 10 ⁹ /L | |
| White blood cell increased (leukocytosis) | - | - | >100,000 mm ³ | Clinical manifestations of leucostasis; urgent intervention indicated | Death |
| Anemia | Hemoglobin (Hgb) <LLN - 10.0 g/dL; <LLN - 6.2 mmol/L; <LLN - 100 g/L | Hgb <10.0 - 8.0 g/dL; <6.2 - 4.9 mmol/L; <100 - 80g/L | Hgb <8.0 g/dL; <4.9 mmol/L; <80 g/L; transfusion indicated | Life-threatening consequences; urgent intervention indicated | Death |
| Lymphocyte count decreased | <LLN - 800/mm ³ ; <LLN - 0.8 x10 ⁹ /L | <800 - 500/mm ³ ; <0.8 - 0.5 x 10 ⁹ /L | <500 - 200/mm ³ ; <0.5 - 0.2 x 10 ⁹ /L | <200/mm ³ ; <0.2 x 10 ⁹ /L | |
| Lymphocyte count increased | - | >4000 - 20,000 mm ³ | >20,000 mm ³ | - | |
| Platelet count decreased | <LLN - 75,000/mm ³ ; <LLN - 75.0 x 10 ⁹ /L | <75,000 - 50,000/mm ³ ; <75.0 - 50.0 x 10 ⁹ /L | <50,000 - 25,000/mm ³ ; <50.0 - 25.0 x 10 ⁹ /L | <25,000/mm ³ ; <25.0 x 10 ⁹ /L | |
| Serum amylase increased | >ULN - 1.5 x ULN | >1.5 - 2.0 x ULN; >2.0 - 5.0 x ULN and asymptomatic | >2.0 - 5.0 x ULN with signs or symptoms; >5.0 x ULN and asymptomatic | >5.0 x ULN and with signs or symptoms | |
| Alkaline phosphatase increased | >ULN - 2.5 x ULN if baseline was normal; 2.0 - 2.5 x baseline if baseline was abnormal | >2.5 - 5.0 x ULN if baseline was normal; >2.5 - 5.0 x baseline if baseline was abnormal | >5.0 - 20.0 x ULN if baseline was normal; >5.0 - 20.0 x baseline if baseline was abnormal | >20.0 x ULN if baseline was normal; >20.0 x baseline if baseline was abnormal | |
| Alanine aminotransferase increased | >ULN - 3.0 x ULN if baseline was normal; 1.5 - 3.0 x baseline if baseline was abnormal | >3.0 - 5.0 x ULN if baseline was normal; >3.0 - 5.0 x baseline if baseline was abnormal | >5.0 - 20.0 x ULN if baseline was normal; >5.0 - 20.0 x baseline if baseline was abnormal | >20.0 x ULN if baseline was normal; >20.0 x baseline if baseline was abnormal | |
| Aspartate aminotransferase increased | >ULN - 3.0 x ULN if baseline was normal; 1.5 - 3.0 x baseline if baseline was abnormal | >3.0 - 5.0 x ULN if baseline was normal; >3.0 - 5.0 x baseline if baseline was abnormal | >5.0 - 20.0 x ULN if baseline was normal; >5.0 - 20.0 x baseline if baseline was abnormal | >20.0 x ULN if baseline was normal; >20.0 x baseline if baseline was abnormal | |

| AE Term | Grade 1 | Grade 2 | Grade 3 | Grade 4 | Grade 5 |
|---------------------------|--|--|--|---|---------|
| Blood bilirubin increased | >ULN - 1.5 x ULN if baseline was normal; > 1.0 - 1.5 x baseline if baseline was abnormal | >1.5 - 3.0 x ULN if baseline was normal; >1.5 - 3.0 x baseline if baseline was abnormal | >3.0 - 10.0 x ULN if baseline was normal; >3.0 - 10.0 x baseline if baseline was abnormal | >10.0 x ULN if baseline was normal; >10.0 x baseline if baseline was abnormal | |
| GGT increased | >ULN - 2.5 x ULN if baseline was normal; 2.0 - 2.5 x baseline if baseline was abnormal | >2.5 - 5.0 x ULN if baseline was normal; >2.5 - 5.0 x baseline if baseline was abnormal | >5.0 - 20.0 x ULN if baseline was normal; >5.0 - 20.0 x baseline if baseline was abnormal | >20.0 x ULN if baseline was normal; >20.0 x baseline if baseline was abnormal | |
| Hemoglobin increased | Increase in >0- 2 gm/dl above ULN | Increase in >2- 4 gm/dl above ULN | Increase in >4 gm/dl above ULN | - | |
| Lipase increased | >ULN - 1.5 x ULN | >1.5 - 2.0 x ULN; >2.0 - 5.0 x ULN and asymptomatic | >2.0 - 5.0 x ULN with signs or symptoms; >5.0 x ULN and asymptomatic | >5.0 x ULN and with signs or symptoms | |
| Hypercalcemia | Corrected serum calcium of >ULN - 11.5 mg/dL; >ULN - 2.9 mmol/L; Ionized calcium >ULN - 1.5 mmol/L | Corrected serum calcium of >11.5 - 12.5 mg/dL; >2.9 - 3.1 mmol/L; Ionized calcium >1.5 - 1.6 mmol/L; symptomatic | Corrected serum calcium of >12.5 - 13.5 mg/dL; >3.1 - 3.4 mmol/L; Ionized calcium >1.6 - 1.8 mmol/L; hospitalization indicated | Corrected serum calcium of >13.5 mg/dL; >3.4 mmol/L; Ionized calcium >1.8 mmol/L; life-threatening consequences | Death |
| Hypocalcemia | Corrected serum calcium of <LLN - 8.0 mg/dL; <LLN - 2.0 mmol/L; Ionized calcium <LLN - 1.0 mmol/L | Corrected serum calcium of <8.0 - 7.0 mg/dL; <2.0 - 1.75 mmol/L; Ionized calcium <1.0 - 0.9 mmol/L; symptomatic | Corrected serum calcium of <7.0 - 6.0 mg/dL; <1.75 - 1.5 mmol/L; Ionized calcium <0.9 - 0.8 mmol/L; hospitalization indicated | Corrected serum calcium of <6.0 mg/dL; <1.5 mmol/L; Ionized calcium <0.8 mmol/L; life-threatening consequences | Death |
| Creatinine increased | >ULN - 1.5 x ULN | >1.5 - 3.0 x baseline; >1.5 - 3.0 x ULN | >3.0 x baseline; >3.0 - 6.0 x ULN | >6.0 x ULN | |
| Hyperglycemia | Abnormal glucose above baseline with no medical intervention | Change in daily management from baseline for a diabetic; oral antiglycemic agent initiated; workup for diabetes | Insulin therapy initiated; hospitalization indicated | Life-threatening consequences; urgent intervention indicated | Death |

| AE Term | Grade 1 | Grade 2 | Grade 3 | Grade 4 | Grade 5 |
|------------------|---|--|---|---|----------------|
| Hypoglycemia | <LLN - 55 mg/dL; <LLN - 3.0 mmol/L | <55 - 40 mg/dL; <3.0 - 2.2 mmol/L | <40 - 30 mg/dL; <2.2 - 1.7 mmol/L | <30 mg/dL; <1.7 mmol/L; life-threatening consequences; seizures | Death |
| Hypophosphatemia | <Laboratory finding only and intervention not indicated | Oral replacement therapy indicated | Severe or medically significant but not immediately life-threatening; hospitalization or prolongation of existing hospitalization indicated | life-threatening consequences | Death |
| Hyperkalemia | >ULN - 5.5 mmol/L | >5.5 - 6.0 mmol/L; intervention initiated | >6.0 - 7.0 mmol/L; hospitalization indicated | >7.0 mmol/L; life-threatening consequences | Death |
| Hypokalemia | <LLN - 3.0 mmol/L | <LLN - 3.0 mmol/L; symptomatic; intervention indicated | <3.0 - 2.5 mmol/L; hospitalization indicated | <2.5 mmol/L; life-threatening consequences | Death |
| Hyponatremia | <LLN - 130 mmol/L | 125-129 mmol/L and asymptomatic | 125-129 mmol/L symptomatic; 120-124 mmol/L regardless of symptoms | <120 mmol/L; life-threatening consequences | Death |
| Hypernatremia | >ULN - 150 mmol/L | >150 - 155 mmol/L; intervention initiated | >155 - 160 mmol/L; hospitalization indicated | >160 mmol/L; life-threatening consequences | Death |
| Hyperuricemia | >ULN without physiologic consequences | - | >ULN with physiologic consequences | life-threatening consequences | Death |

